8.6.3 Local Laboratory Processing of Samples – Flow Cytometry

Optional flow-cytometry analysis of tissues will be conducted on a selected subset of subjects enrolled and biopsied. Approximately 4 fresh samples will be placed into a MACS-buffered solution for tissue dissociation. Additional specifications for tissue preparation and cell sorting for flow cytometric analysis can be found in the NAV3-32 Pathology Manual.

8.7 Safety

8.7.1 Adverse Events

8.7.1.1 Definition of Adverse Event

The definitions below follow International Conference on Harmonization (ICH) – Good Clinical Practice (GCP) (see also ICH Guideline for Clinical Safety Data Management: Definitions and Standards for Expedited Reporting).

An AE is defined as any untoward medical occurrence in a subject administered a pharmaceutical product and which does not necessarily have a causal relationship with this treatment. An AE can therefore be any unfavorable and unintended sign (including an abnormal laboratory finding), symptom, or disease temporally associated with the use of a medicinal (investigational) product, whether or not considered drug related.

Any clinically significant change in a condition (worsening) from screening that results in a change in subject management will be considered an AE and will be recorded on the AE page of the CRF.

For this study, all untoward medical occurrences beginning on the Visit 2 (Day 0) until the final Follow-up Telephone Safety Assessment (Visit 5) are to be reported as AEs. AEs continuing after study completion will be followed to normalization or stabilization. Additionally, untoward medical events occurring prior to the day of Tc 99m tilmanocept administration will be collected and added to the subject's medical history unless they are related to a study procedure in which case the event will be recorded as an AE. SAEs will be reported from the time of consent through the end of participation.

8.7.1.2 Categories for Adverse Event Assessment

The severity of an AE is classified according to the following categories, taking into account the possible range of the intensity of the event:

- Mild The adverse event is transient and easily tolerated by the subject.
- Moderate The adverse event causes the subject discomfort and interrupts the subject's usual activities
- Severe The adverse event causes considerable interference with the subject's usual activities and may be incapacitating or life-threatening.

Specific drug treatment

Any specific drug treatment administered for an AE will be documented.

Causal relationship to investigational product

The investigator will use the following definitions to assess the relationship of the adverse event to the use of investigational product:

Definitely related: Event can be fully explained by administration of the investigational product.

Probably related: Event is most likely to be explained by administration of the investigational product rather than the subject's clinical state or other agents/therapies.

Possibly related: Event may be explained by administration of the investigational product or by the subject's clinical state or other agents/therapies.

Probably not related: Event is most likely to be explained by the subject's clinical state or other agents/therapies, rather than the investigational product.

Definitely not related: Event can be fully explained by the subject's clinical state or other agents/therapies.

For causality assessments, events meeting the categories of definitely, probably, or possibly related will be considered to be related to investigational product.

Causal relationship to study procedure

The investigator will use the following definitions to assess the relationship of the adverse event to study procedure:

Definitely related: Event can be fully explained by the study procedure.

Probably related: Event is most likely to be explained by the study rather than the subject's clinical state or other agents/therapies.

Possibly related: Event may be explained by the study procedure or by the subject's clinical state or other agents/therapies.

Probably not related: Event is most likely to be explained by the subject's clinical state or other agents/therapies, rather than the study procedure.

Definitely not related: Event can be fully explained by the subject's clinical state or other agents/therapies.

For causality assessments, events meeting the categories of definitely, probably, or possibly related will be considered to be related to study.

8.7.1.3 Assessments and Documentation of Adverse Events

Attention shall be paid to the occurrence of AEs for the duration of subject participation. Events occurring prior to Visit 2 (Day 0) will be recorded in the subject's medical history unless they are related to a study procedure in which case the event will be recorded as an AE. Untoward medical events beginning on Visit 2 (Day 0) through the completion of the Visit 5 Follow-up Telephone Safety Assessment will be reported as adverse events. SAEs will be reported from the time of consent through the end of participation.

Any AE (observed, volunteered, or elicited) should be recorded in detail in the source documentation.

The following information is required:

- The **date and time of onset** of any AE.
- The **duration** (the entire duration of an event or symptom, calculated from date of onset to date of end, if not recorded directly).
- The **seriousness** of the AE will be assessed by the investigator. If the investigator deems that an AE qualifies as an SAE, a special form provided by the sponsor should be completed and the event must be immediately reported to the sponsor. A definition of serious adverse events is provided in [Section 8.7.1.5](#).
- The maximum **severity** (mild, moderate, or severe).
- If drug treatment was administered for the event, specific concomitant medication must be documented.
- The **relationship** of the AE to the investigational product and to study conduct (for definitions, see above).
- The **outcome** of the AE (resolved, resolved with sequelae, not resolved, unknown, death).

AEs will be coded according to an internationally recognized dictionary (Medical Dictionary for Regulatory Activities [MedDRA]).

8.7.1.4 Expected Adverse Events

Investigational Product-Related Risks

In all completed studies of Lymphoseek (Tc 99m tilmanocept), involving 553 subjects, only 3 events (breast pain and injection site pain reported by subjects with breast cancer and injection site irritation reported by a subject with head and neck squamous cell cancer) were deemed definitely related to the administration of Lymphoseek by the investigator. The most common adverse reactions (incident < 1%) have been lack of effect (< 0.067%), injection site pain (< 0.02%) and rash (< 0.02%). Adverse events from the radioactive dose are not expected, since the applied radiation doses are far below doses that can cause acute effects in human tissues.

In addition to the Lymphoseek pre-approval clinical studies, post-marketing surveillance shows that Lymphoseek has been administered to more than 300,000 patients with not a single drug-related SAE. Routes of administration included: subcutaneous, intradermal, and peritumoral. The intended route of administration in this study is intravenous. There have been over 135IV administrations of Tc 99m tilmanocept and no SAEs or adverse drug reactions (ADRs) have been reported to date.

Risks of Imaging Procedures

Radiation dose considerations from Tc 99m Tilmanocept planar scans – Subjects enrolled in this trial will have a hand/wrist planar gamma camera scan following Tc 99m tilmanocept injection.

The average effective radiation dose per 10 mCi Tc 99m tilmanocept injection is calculated to be 2.7 mSv (equivalent to about ten months of natural background radiation received in the US). Subjects enrolled in this study will receive one injection, equal to 2.7 mSv total. This is considered to be a minor to intermediate risk level corresponding to the benefit to the patient (category IIb based on the International Commission on Radiological Protection 62 (ICRP62)) and is balanced against the possible substantial societal benefit that can be gained from the trial (European Commission Radiation Protection 99, 1998 and ICRP 62, 1992). For further reference, the effective dose from a standard computed tomography (CT) abdomen and pelvis, with and without contrast, is up to 20 mSv.

Precautionary Measures

Special precautionary measures are not considered necessary for this study. In case of emergency, standard emergency procedures will be employed.

Unexpected Adverse Events

An unexpected adverse event is defined as an adverse reaction that in nature and severity is not consistent with the applicable product information (e.g., Investigator's Brochure). Any adverse experience that is not listed in the current Investigator's Brochure or which is, with regard to the specificity or severity, not consistent with the risk information shall be regarded as unexpected.

Examples would be (a) acute renal failure listed in the Investigator's Brochure with a subsequent new report of interstitial nephritis and (b) hepatitis with a first report of fulminant hepatitis. "Unexpected" as used in this definition refers to an adverse drug experience that has not been previously observed and included in the Investigator's Brochure, rather than from the perspective of such experience not being anticipated from the pharmacological properties of the investigational product.

8.7.1.5 Serious Adverse Events

Definition of Serious Adverse Events

The following SAE definition is based on ICH guidelines and the final rule issued by the Food and Drug Administration (FDA) and effective 06 Apr 1998.

An SAE is classified as any untoward medical occurrence that at any dose:

- results in death, or
- is life threatening, or
- requires inpatient hospitalization or prolongation of existing hospitalization, or
- results in persistent or significant disability/incapacity, or
- is a congenital anomaly/birth defect, or

- is an important medical event (see paragraphs below).

The term ‘life threatening’ in the definition refers to an event in which the subject was at risk of death at the time of the event; it does not refer to an event that hypothetically might have caused death if it were more severe.

Medical and scientific judgment should be exercised in deciding whether it is appropriate to report an AE as serious also in other situations, such as important medical events that may not be immediately life threatening or result in death or hospitalization but may jeopardize the subject or may require intervention to prevent one of the other outcomes listed in the definition above. These should also usually be considered serious. Examples of such events are intensive treatment in an emergency room or at home for allergic bronchospasm or blood dyscrasias or convulsions that do not result in subject hospitalization.

Actions and reporting obligations in case of serious adverse events

The investigator should take appropriate diagnostic and therapeutic measures to minimize the risk to the subject.

If any SAE occurs over the course of the study, investigators or other site personnel will inform Navidea Biopharmaceutical representatives within 1 day (i.e., within 24 hours) of becoming aware of the SAE. Written notification of the SAE will be emailed to Navidea Biopharmaceuticals Pharmacovigilance at [contact]. For fatal or life-threatening adverse events where important or relevant information is missing, active follow-up is undertaken immediately.

Pregnancy will have the same time reporting obligations to the sponsor as SAEs. Upon notification, Navidea will provide a form for collection of pregnancy information.

All SAEs must also be recorded on the Adverse Event eCRFs.

Notification of the IRB(s)/IEC(s)

The sponsor and/or the investigator will notify the IRB(s)/IEC(s) about all relevant events (e.g., serious adverse events [SAEs] and Suspected, Unexpected, Serious Adverse Reactions [SUSARs]) according to all applicable regulations.

Notification of the authorities

The sponsor will process and report all relevant events (e.g., SAEs, SUSARs) to the authorities according to all applicable regulations.

Sponsor’s notification of the investigators

The sponsor will inform all investigators about reported relevant events (e.g., SAEs, SUSARs) according to all applicable regulations.

8.7.2 Vital Signs

Vital signs comprise the measurement of body temperature, heart rate, respiration, and systolic and diastolic blood pressure. All measurements will be taken after the subject has been in a resting position for at least 1 minute. Vital signs will be measured at screening, within 30 minutes before investigational product administration, and within 30 minutes after investigational product administration (after the ECG assessment during this 30-minute post-Tc 99m tilmanocept interval). Any clinically significant change from screening (worsening) that results in a change in subject management will be considered an AE and will be recorded on the AE page of the CRF.

8.7.3 Electrocardiogram

A standard 12-lead ECG will be obtained up to 30 minutes before investigational product administration and within 30 minutes after investigational product administration. The ECG will be measured with the subject in a resting position for at least 1 minute. Continuous ECG monitoring is not required. At a minimum, the heart rate, QRS, PR, and QT intervals will be collected. QTc will be calculated using the Fridericia formula.

On-site investigator's responsibilities

The immediate cardiac safety of the subject will be ensured by the on-site qualified physician. Any 12-lead ECG intervals, waveform abnormalities, and rhythm changes that are clinically significant in that they result in a change in subject management will be considered an AE. In the case of an SAE, once SAE notification is decided upon, investigators are required to follow the procedure described for SAE notification and document abnormal ECG findings (intervals and waveforms). Any interval data or abnormal waveform finding that resulted in an AE (i.e., change of patient management) must be followed to normalization or stabilization. Each 12-lead ECG tracing must be signed and dated and stored in the subject's source documentation.

8.7.4 Clinical Laboratory Parameters

Table 5 Clinical Laboratory Parameters

Hematology	Hemoglobin (Hgb), hematocrit (Hct), platelets, neutrophils, basophils, lymphocytes, monocytes, red blood cells (RBC), white blood cells (WBC)
Serum chemistry	Aspartate aminotransferase (AST), alanine aminotransferase (ALT), alkaline phosphatase, total bilirubin, creatinine, chloride, potassium, sodium, total protein, albumin, carbon dioxide (CO ₂)/bicarbonate, blood urea nitrogen (BUN), glucose
Urinalysis	pH, specific gravity
Rheumatoid Panel	Erythrocyte sedimentation rate (ESR), C-reactive protein (CRP), rheumatoid factor (RF); anti-citrullinated peptide antibody (ACPA)

All laboratory reports must be promptly reviewed for clinical significance by the investigator, and upon review, initialed and dated by the investigator.

Good clinical practice would suggest that a copy of the laboratory results also be provided to the subject's referring physician.

Only abnormal laboratory values will be collected in the electronic database. Any change in a laboratory value, which results in a change in subject management (additional controls or treatment required), will be reported as a clinically significant change. Clinically significant changes in laboratory parameters that are not the result of laboratory error are to be recorded as AEs.

Any clinically significant changes in laboratory values are to be followed up with repeated tests at appropriate intervals (as determined by the investigator) until the values return to baseline level or until the abnormality is explained by the investigator. The expected amount of blood to be drawn is shown in Table 6.

Table 6 Approximate Amount of Blood Drawn per Subject

Timepoint	Test (Sample Volume)	Total Blood Drawn at Timepoint
Visit 1 (Day -30 to -1)	Chemistry (5 mL) Hematology (4 mL) RA panel (4 mL)	13 mL (2.6 teaspoons)
Visit 2 (Day 0)	Chemistry (5 mL) Hematology (4 mL)	9 mL (1.8 teaspoons)
TOTAL		22 mL (4.5 teaspoons)

9 PLANNED STATISTICAL METHODS

This study is a Phase 2b, prospective, open-label, multicenter study of the patterns of association between quantitative Tc 99m tilmanocept planar imaging and synovial histopathology in subjects clinically diagnosed with RA.

Subjects will undergo an imaging assessment followed by an ultrasound-guided synovial biopsy of a selected joint in a subsequent visit. Tissue samples from the synovial biopsy procedure will be used for 2 mandatory anatomic pathology evaluations:

- IHC and immunofluorescence imaging targeting various immune markers associated with inflammatory disease; and,
- RNA-sequencing to provide transcriptional profiling of pathotype-specific gene expression profiles.

Optional flow cytometry will be performed by a local pathology laboratory with a subset of subjects for the exploratory analysis of TUV_{joint} and the number and size of CD68, CD163, and CD206.

Results from each of the 3 anatomic pathology evaluations will be correlated with $TUVs$ on planar imaging to mechanistically assess the relationship between synovial anatomic pathology and TUV . These evaluations will provide quantitative and semi-quantitative information regarding joint-specific disease activity.

9.1 Randomization Methods

This study is not randomized.

9.2 Safety Variables

The safety analysis variables are defined as follows:

- Adverse Events (AEs)
- Clinical Laboratory Tests (hematology, serum chemistry, urinalysis)
- ECG Parameters
- Vital Signs

9.3 Efficacy Variables

The primary efficacy variables for this study are defined below:

- Tc 99m tilmanocept uptake values (TUV_{joint}) for the biopsied joints;
- IHC assessment of macrophage expression of the CD206 receptor.

The secondary variables for this study are defined below:

- IHC and immunofluorescence assessment of macrophage expression and co-expression of the CD68 and CD163 receptors;
- Pathotype classification of RA disease as lympho-myeloid, diffuse myeloid, or pauci-immune fibroid, based on TUV_{joint} .

The exploratory efficacy variables for this study are defined below:

- IHC assessment of macrophage expression of the CD3, CD20, CD55, and TE7 biomarkers;
- mRNA levels in synovial tissue for the CD206, CD163, and CD68 biomarkers;
- Flow cytometry measurements of CD206, CD163, and CD68 biomarker expression and co-expression.
- IHC assessment of the expression of a biomarker (e.g., CD206, TE7) is determined from immunofluorescent microscopy, specifically:
 - The ratio of the total fluorescent stained area to the total field area under 4x and 10x power magnification.

All IHC assessments will be done at a single laboratory in accordance with the laboratory SOPs.

- Classification of synovial anatomic pathology into lympho-myeloid, diffuse myeloid, and pauci-immune fibroid types using a multinomial logistic regression model with TUV_{global} as a covariate.
- Tc 99m tilmanocept global uptake values (TUV_{global}) per subject.

It is presumed that the presence of radiotracer uptake for a joint indicates the presence of activated macrophages. The use of the term “localization” is synonymous with radiotracer uptake.

TUV is defined as:

$$TUV_{ROI} = \frac{\bar{X}_{joint}}{\bar{X}_{RR}};$$

where

- \bar{X}_{joint} is the average pixel intensity of a region of interest (ROI) of a subject at the time of imaging (nominally 60 minutes);
- \bar{X}_{RR} is the average pixel intensity of the reference region (RR) of a subject at the time of imaging (nominally 60 minutes).

Calculation of TUV_{joint} and TUV_{global} are further described in the study statistical analysis plan (SAP).

9.4 Sample Size and Justification

The sample size is expected to be approximately 12 to 24 joints. The final sample size will be determined after the completion of an interim analysis including at least 4 subjects in each pathotype (diffuse myeloid, lympho-myeloid and pauci-immune fibroid). The final sample size will be chosen on the basis of the sponsor's business requirements regarding precision for the estimated correlation between CD206 expressing macrophage density and TUV_{joint}. The final sample size will be at least N = 12. If the rarest pathotype has 25% prevalence in the study patient pool, the expected number of subjects at the interim analysis is N = 16. These needs may be further increased because synovial biopsy fails to recover enough tissue for histological analysis in about 15% of cases ([Wechalekar 2014](#)).

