In recent years, synovial biopsy-enabled studies have greatly increased our understanding of the pathological processes occurring within the inflamed joints of RA patients (Orr 2017). An important finding of these studies has been that the inflammatory cell compositions of RA inflamed joints can vary between patients (Townsend 2014, van de Sande 2016). The biopsy specimens obtained from different RA patients can have different numbers and densities of macrophages and monocytes, lymphocytes and lymphocyte containing structures, and fibroblast-like synoviocytes (Orr 2017). These differences in cellular composition suggest that RA inflammation can be divided into 3 pathotypes, referred to as diffuse myeloid, lympho-myeloid, and fibroid, respectively (Dennis 2014, Astorri 2015). High densities of macrophages can occur in both the myeloid and lymphoid pathotypes, whereas the fibroid pathotype is largely devoid of both macrophages and lymphoid cells. These pathotypes are not fully discrete, with some overlap occurring. However, they provide a strong basis for temporal or cytological compartmentalization in RA disease natural history.

Current studies utilizing IHC analyses of synovial biopsies are insufficient to determine the distribution of the various pathotypes in RA patients but suggest that the diffuse myeloid and lympho-myeloid pathotypes are about equally frequent in RA patients with the fibroid pathotype being less common. There is growing evidence that patients with different RA pathotypes respond differently to various therapies, holding out the possibility that determining the RA pathotype of an individual patient's RA can direct the choice of the most effective therapy for that patient (i.e., personalized RA therapy) (Dennis 2014). This is an area of ongoing active investigation in RA therapy research (Pitzalis 2013, Donlin 2018, Mandelin 2018). However, already there is significant evidence indicating that patients with a myeloid-

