8 PROCEDURES AND VARIABLES

8.1 Population Characteristics

8.1.1 Demographics and Other Baseline Characteristics

Twelve (12) to 24 evaluable subjects may be enrolled. Subjects will be men and women aged ≥ 18 years with clinically diagnosed RA who are on stable therapy.

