9.5.6 Interim Analysis

An interim analysis will be performed after 4 subjects in each of the 3 pathotypes (diffuse myeloid, lympho-myeloid, and pauci-immune fibroid) have been imaged. Specific analyses will be described in the study SAP (or interim analysis plan [IAP]) and will include computation of the product-moment and rank correlations between TUV_{joint} and CD206 expressing macrophage count (defined in [Section 9.5.3.1](#)). Additional analyses may be described in the study IAP (if written) or SAP (if no IAP is written). The final sample size will be recalculated after completion of the interim analysis.

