### **1.3 Sample Size**

The sample size is expected to be approximately 12 to 24 joints. The final sample size will be determined after the completion of an interim analysis including at least 4 subjects in each pathotype (diffuse myeloid, lympho-myeloid and pauci-immune fibroid). The final sample size will be chosen based on the sponsor's business requirements regarding precision for the estimated correlation between CD206 expressing macrophage density and  $TUV_{joint}$ . The final sample size will be at least  $N = 12$ . If the rarest pathotype has 25% prevalence in the study patient pool, the expected number of subjects at the interim analysis is  $N = 16$ . These needs may be further increased because synovial biopsy fails to recover enough tissue for histological analysis in about 15% of cases.

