## 2.4 Interim Analyses

An interim analysis will be performed after 4 subjects in each of the 3 pathotypes (diffuse myeloid, lympho-myeloid, and pauci-immune fibroid) have been imaged. The final sample size will be recalculated after completion of the interim analysis.

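### The expected interim size of 16 is the wait for the rarest pathotype alone; filling all three pathotypes takes about 18.6 to 20.6 evaluable subjects on average

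*Protocol*

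**What the plan says.** Protocol 9.4 gives a planned size of roughly 12 to 24 joints and leaves the final number until after "an interim analysis including at least 4 subjects in each pathotype". Protocol 9.5.6 repeats the timing rule: "An interim analysis will be performed after 4 subjects in each of the 3 pathotypes" have been imaged. SAP 1.3 and 2.4 carry the same rule, and SAP 2.4 adds that "The final sample size will be recalculated after completion of the interim analysis".

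One figure is given for when this will happen. SAP 1.3 puts the condition as "If the rarest pathotype has 25% prevalence in the study patient pool", and both documents conclude that "the expected number of subjects at the interim analysis is N = 16". No formula is shown, and neither section gives prevalences for the other two pathotypes.

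The next sentence says the requirement may rise because "synovial biopsy fails to recover enough tissue for histological analysis in about 15% of cases". The 16 is therefore a count before biopsy losses, and no inflated count follows. Protocol 8.1.1 states the planned range in evaluable terms: "Twelve (12) to 24 evaluable subjects may be enrolled".

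On the pathotype mix, Protocol 1.1 says "Current studies utilizing IHC analyses of synovial biopsies are insufficient to determine the distribution of the various pathotypes in RA patients", though it adds that the two myeloid types look similarly common and the fibroid type less so.

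**The concern.** The trigger is a condition on three counts, but 16 is what comes out when only one count is considered. The wait for all three classes to reach 4 is the longest of three waits. Its mean cannot be below the mean wait for the rarest class, and it is strictly greater whenever another class can be the last to fill.

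This matters for planning. It is the only figure the documents give for the timing of the analysis that sets the final sample size. A figure that is too low makes the interim look earlier than it will be, and makes the remainder of the 12 to 24 range look larger than it will be when the sample size is recalculated.

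**Working it through.** **Inputs.** Trigger: 4 in each of 3 pathotypes (Protocol 9.4 and 9.5.6; SAP 1.3 and 2.4). Rarest prevalence: 0.25 (Protocol 9.4, SAP 1.3). Biopsy failure: 0.15 (Protocol 9.4). Upper end of the range: 24 evaluable subjects (Protocol 8.1.1). The split of the remaining 75% is not given. Because 25% is the rarest class, each of the others is at least 25%, so the split lies between 37.5/37.5 and 25/50.

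**Reproducing the plan's figure.** The mean wait for k subjects of a class with prevalence p is k/p = 4/0.25 = 16.0. This matches the stated 16 exactly and involves one class only.

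**Expected size under the stated rule.** Let s = (s1, s2, s3) be the numbers still needed in each class. With independent enrolment at fixed prevalences p1, p2, p3, the expected number of further evaluable subjects is

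E(s) = [1 + Σ p_i · E(s − e_i)] / Σ p_i,

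with both sums over classes not yet full, e_i one subject in class i, and E(0,0,0) = 0. The quantity wanted is E(4,4,4). The probability that the trigger is met by n subjects is the multinomial probability that all three counts are at least 4.

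| Split (%) | Mean | Median | Met by 16 | Not met by 24 |
|---|---|---|---|---|
| 25 / 37.5 / 37.5 | 18.57 | 17 | 43.5% | 12.9% |
| 25 / 30 / 45 | 19.22 | 18 | 38.1% | 15.7% |
| 25 / 25 / 50 | 20.57 | 19 | 29.5% | 22.5% |

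Simulation of 200,000 trials gave means of 18.56 (first row) and 20.56 (last row).

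**Shortfall.** 18.57 − 16 = 2.6 and 20.57 − 16 = 4.6 evaluable subjects.

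**How much is chance in the rarest class.** Its own wait exceeds 16 with probability P(Bin(16, 0.25) ≤ 3) = 40.5%, and exceeds 24 with probability P(Bin(24, 0.25) ≤ 3) = 11.5%. At the equal split, most of the 12.9% risk of passing 24 is therefore present even on the one-class view.

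**Biopsied subjects at 15% failure.** Stated basis: 16/0.85 = 18.8. Corrected: 18.57/0.85 = 21.8 to 20.57/0.85 = 24.2. The gap is 3.0 to 5.4.

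**Room left below 24 evaluable.** Stated basis: 24 − 16 = 8. Corrected: 24 − 18.57 = 5.4, down to 24 − 20.57 = 3.4.

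**Sensitivity to the 25% premise.** 30/35/35 gives 17.4 and 20/40/40 gives 21.4. Equal thirds, the most favourable mix possible, gives 17.2, still above 16.

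**The case against.** The arithmetic is hard to dispute, so the case on the other side concerns its size and consequences.

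- **The split.** Protocol 1.1 describes the two myeloid types as similarly frequent and the fibroid type as less common. That points to the 18.6 end; 20.6 needs a second pathotype tied at 25%. This stands as a reason to read 18.6 as the likelier value and 20.6 as a bound. It does not remove the range, because the same sentence calls the evidence insufficient to settle the distribution, and 18.6 is still 2.6 above the stated figure.
- **The spread.** At the equal split the median is 17, one above 16, and the standard deviation of the trigger point is about 5.5, so the shift is about half a standard deviation. This is true, and it limits the practical effect. But the documents state an expectation, and neither the mean nor the median is 16 at any split with a 25% rarest class.
- **The ceiling.** The planned range is approximate and no rule stops enrolment at 24. This is fair: the lost room is a planning consequence, not a breached limit.
- **The failure rate.** Protocol 1.1 cites 5% to 10% inadequate tissue, against 15% in section 9.4. At the equal split the lower rates give 18.57/0.95 = 19.5 to 18.57/0.90 = 20.6 biopsied. The 15% is used here because the sample size section itself uses it.
- **No analysis uses the figure.** This is correct, and it keeps the point to a correction of the planning text.

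**Conclusion.** The concern holds. Under the trigger that both documents state, the expected interim size at a 25% rarest pathotype is 18.6 to 20.6 evaluable subjects. The stated 16 answers a narrower question and is 2.6 to 4.6 too low (3.0 to 5.4 in biopsied subjects at 15% failure). The lower end is the better supported by the Protocol's own background.

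The result assumes independent enrolment at fixed prevalences, an interim at the first moment all three classes reach 4, no other pathotype below 25%, and biopsy failure unrelated to pathotype. The first is also the model behind 4/0.25.

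The consequence is limited to planning: interim timing and the apparent room for the sample size recalculation. Because the trigger depends on counts, the interim still takes place when the classes fill, and the primary correlation analysis does not change. The figure should be corrected, since it is wrong in both documents and is the only one given.

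**What to change.** In Protocol 9.4 and SAP 1.3, replace the sentence giving 16 with wording such as:

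> *With a rarest-pathotype prevalence of 25%, about 19 to 21 evaluable subjects (about 22 to 24 biopsied, allowing 15% biopsy failure) are expected before 4 are available in each pathotype, depending on the split of the other two.*

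Reword the opening of the following sentence to say that the biopsied figure is higher because of tissue failure, so that the 15% is not applied a second time. Leave the trigger of 4 per pathotype as it is.

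The cost is one sentence replaced and the start of another reworded in each document. No patients, data or analyses are added, and the design does not change.
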